## 8.3.4. Pregnancy Testing

Pregnancy testing should be done if menstruation stops or becomes irregular. If pregnancy is confirmed, the participant should be withdrawn from the study.

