### **Medical conditions**

- 1. Ongoing treatment for active malignant disease
- 2. Severe hepatic or renal disease
- 3. Sever psychiatric disease
- 4. Chronic abuse of alcohol or drug abuse
- 5. Current pregnancy, and if the participant plan to become pregnant during the 12 months of study participation.
- 6. Known hypersensitivity to the active substance or any of the excipients.

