# 7.2. Participant Discontinuation/Withdrawal from the Study

- A participant may withdraw from the study at any time at the participant's own request for any reason (or without providing any reason).
- A participant may be withdrawn at any time at the discretion of the investigator for safety reasons.
- At the time of discontinuing from the study, if possible, an early discontinuation visit should be conducted, as shown in the SoA. See SoA for data to be collected at the time of study discontinuation and follow-up and for any further evaluations that need to be completed.
- The participant will be permanently discontinued from the study intervention and the study at that time.
- If the participant withdraws consent for disclosure of future information, the sponsor may retain and continue to use any data collected before such a withdrawal of consent.
- If a participant withdraws from the study, the participant may request destruction of any samples taken and not tested, and the investigator must document this in the site study records.

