### Visits 5 and 6 - 6 and 12 months (tasks for the recruiting physician)

- Physician/ nurse: Interview the patient on the effect of the medication by filling out the adrenal insufficiency form in Noklus Diabetes. Review dosing/ compliance, extra doses, side-effects, use of self-injection, and adrenal crises management.
- Regular blood chemistry including hemoglobin, Erythrocyte volume fraction, leucocytes, thrombocytes, creatinine, Na, K, calcium, magnesium, alanine amino transferase.
- Biobanking: serum and EDTA, urine, saliva (0,1 and 4 hours after morning dose), and hair examples.
- Patient: PROMS, including HRQoL questionnaires. At visit 5 or 6: Sleep diary actipragphy and sleep radar.

© 2015-2021 TransCelerate BioPharma

Doc. No. CT 2.01.01. Valid from 31 Jan 2022. Only the electronic version is valid.

Page 32 of 65

• At visit 6: Bone mineral density measurement, body composition, and measure bone markers as well as vitamin D.

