## 8.4.1. Time Period and Frequency for Collecting AE and SAE Information

All SAEs and AEs will be collected from the start of study intervention until visit 6 at the time points specified in the SoA (Section 1.3).

All SAEs will be recorded and reported to the sponsor or designee immediately and under no circumstance should this exceed 24 hours, as indicated in Appendix [3/7]. The investigator will submit any **updated SAE data to the sponsor within 24 hours** of it being available.

Investigators are not obligated to actively seek information on AEs or SAEs after conclusion of the study participation. However, if the investigator learns of any SAE, including a death, at any time after a participant has been discharged from the study, and the investigator considers the

© 2015-2021 TransCelerate BioPharma

Doc. No. CT 2.01.01. Valid from 31 Jan 2022.

Only the electronic version is valid.

Page 39 of 65

event to be reasonably related to the study intervention or study participation, the investigator must promptly notify the sponsor.

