### 8.4.5. Pregnancy

Pregnancy at screening and planned pregnancy during the duration of study
participation is an exclusion criteria. However, all AD patients (including all study
participants) need to continue using one of the study drugs throughout the pregnancy
as cortisol is a hormone necessary for survival in this patient group. The two study
drugs in this study are the only approved treatment options in Norway. Therefore,

© 2015-2021 TransCelerate BioPharma

Doc. No. CT 2.01.01. Valid from 31 Jan 2022. Only the electronic version is valid.

Page 40 of 65

study participants who become pregnant during this trial will not be discontinued from study treatment.

- Pregnant AD patients may need alterations of doses which will be performed by local study investigators independently of study participation.
- If a pregnancy is reported during the study, the investigator will record pregnancy information in the appropriate form and submit it to the sponsor.
- While pregnancy itself is not considered to be an AE or SAE, any pregnancy complication or elective termination of a pregnancy for medical reasons will be reported as an AE or SAE.
- Abnormal pregnancy outcomes (e.g. spontaneous abortion, fetal death, stillbirth, congenital anomalies, ectopic pregnancy) are considered SAEs and will be reported as such.

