## 10. Supporting Documentation and Operational Considerations

# 10.1. Appendix 1: Regulatory, Ethical, and Study Oversight Considerations

The study will be performed in accordance with the protocol, the World Medical Association Revised Declaration of Helsinki (2008), the ICH Harmonized Tripartite Guideline for Good Clinical Practice, and any local regulations. The Ethics committee for medical research, Western Norway has granted permission to conduct the trial (ADNorGC). The patient will receive oral and written information concerning the study.

ROAS have ethical approval (REK 2013/1504) and is licensed by the Norwegian Data Protection Authority (1). This specific project was submitted to IEC in mid-2021, and an ethical approval has been obtained. Likewise, the project will be registered in the ClinicalTrials.gov database prior to study start.

All participants will receive thorough oral and written information before providing written consent for study participation. The participants are free to withdraw their consent at any time during the study. Clinical records and results will be archived in hospital records. Data will be collected to computerized research files without patient identifiers and stored according to the hospitals' research ethics guidelines. Biological research materials (blood samples) are coded and stored at laboratory at Haukeland University Hospital according to general regulations, D

Patients will be instructed to report any adverse events during the study period to the recruiting physician. If a patient develops conditions meeting the exclusion criteria or serious adverse events, the patient will be withdrawn from the study. The recruiting physician may also discontinue study participation at any time if it is considered necessary for any of the following reasons:

- Significant protocol deviation or violation.
- Significant failure to comply with study requirements.

Deviation log: We encourage doctors in charge of patients to report all deviations in the protocol to the coordinating investigator or medical monitor, as well as to register in the patient journal.

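### The rules for a participant who becomes pregnant contradict each other, and nothing requires a reported pregnancy to be followed to its outcome

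*Protocol*

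**What the plan says.** Five places in the protocol bear on a pregnancy during the trial.

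- **Section 8.3.4 (Pregnancy Testing):** "If pregnancy is confirmed, the participant should be withdrawn from the study".
- **Section 10.1 (Appendix 1):** "If a patient develops conditions meeting the exclusion criteria or serious adverse events, the patient will be withdrawn from the study". Exclusion criterion 5 in section 5.2 reads "Current pregnancy, and if the participant plan to become pregnant during the 12 months of study participation", so a pregnancy during the trial triggers this rule too.
- **Section 7.2 (Withdrawal from the Study):** "The participant will be permanently discontinued from the study intervention and the study at that time".
- **Section 8.4.5 (Pregnancy):** "study participants who become pregnant during this trial will not be discontinued from study treatment". The reason given is that a study drug is needed for survival. The section adds: "Pregnant AD patients may need alterations of doses which will be performed by local study investigators independently of study participation". It requires a pregnancy form to be sent to the sponsor and classes abnormal outcomes, from spontaneous abortion and ectopic pregnancy to stillbirth and congenital anomalies, as reportable SAEs.
- **Section 8.4.1 (AE/SAE collection period):** "All SAEs and AEs will be collected from the start of study intervention until visit 6". Section 8.1.3 places visit 6 at 12 months. Investigators need not actively look for events once participation has ended, but they must notify a later SAE that they learn of and consider reasonably related.

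The Schedule of Activities also marks AE and SAE review at visit 7 (end of study), a visit for which it gives no day. The synopsis counts six visits.

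**The concern.** There are two problems, and both are site instructions that belong in the protocol rather than in a statistical analysis plan.

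The first is the contradiction. Taken literally, sections 8.3.4 and 7.2 together take a pregnant participant off study intervention, and section 8.4.5 says this will not happen. Investigators who start from different sections could act differently on treatment. They could also differ on participation, if some take continued study treatment to mean continued participation. HRQoL, weight and cortisol data after a pregnancy would then depend on which section was consulted.

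The second is the safety record. Section 8.4.5 undertakes to report abnormal outcomes, some of which can be known only at delivery. The active collection period is tied to the study calendar and not to the pregnancy. Nothing obliges the site to find out how the pregnancy ended.

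The situation is foreseeable. Entry starts at age 16, the introduction says that the disease affects more women than men and often the young, and only current or planned pregnancy is excluded.

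**Working it through.** The protocol states no figure on this point, so there is none to reproduce. The check has two parts.

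**1. Can all the provisions be followed at once?**

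| Provision | Study participation | Study treatment |
|---|---|---|
| 8.3.4 | ends | not mentioned |
| 10.1 with exclusion criterion 5 | ends | not mentioned |
| 7.2 (general rule on leaving) | ends | ends permanently |
| 8.4.5 | not stated | continues |

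Sections 8.3.4 and 8.4.5 are compatible when read alone, because one concerns the study and the other the treatment. Section 7.2 removes that separation: leaving the study also ends the study intervention. So 8.3.4 plus 7.2 gives treatment ended, and 8.4.5 gives treatment continued. Section 10.1 plus 7.2 produces the same clash. Section 10.1 also withdraws a participant for an SAE, so an abnormal outcome, which 8.4.5 classes as an SAE, would trigger withdrawal a second time.

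**2. What share of outcomes falls after visit 6?**

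Inputs:
- Collection window: day 0 to day 365 (visit 6 in the Schedule of Activities).
- Day of conception, C: uniform on 0 to 365. This is an assumption; the protocol gives no pregnancy rate or timing.
- Days from conception to outcome, g: assumed, and varied below.
- The participant stays in the study until visit 6.

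Formula: the outcome falls after visit 6 when C + g > 365, so the share is g / 365.

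| Outcome at | g (days) | Last conception day inside the window (365 − g) | Share after visit 6 (g / 365) |
|---|---|---|---|
| Loss 6 weeks after conception | 42 | 323 | 11.5% |
| Loss 10 weeks after conception | 70 | 295 | 19.2% |
| 18 weeks after conception | 126 | 239 | 34.5% |
| 26 weeks after conception | 182 | 183 | 49.9% |
| 35 weeks after conception | 245 | 120 | 67.1% |
| Term, 38 weeks after conception | 266 | 99 | 72.9% |

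Term and near-term outcomes therefore fall mostly after the window, and early losses mostly inside it.

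If 8.3.4 is applied instead, participation ends at confirmation of the pregnancy. Any outcome that follows confirmation then falls after active collection has ended, which is nearly all of them.

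**The case against.** The strongest defence of the text is that treatment and participation can separate in this trial. Both drugs are marketed, prescribed and dispensed as in ordinary care, and section 7.1 says replacement is needed at all times. Section 8.4.5 speaks of dose changes made independently of study participation, which fits a participant who has left the study and keeps her drug. On participation itself the protocol is consistent: 8.3.4 and 10.1 both withdraw, and no section says that a pregnant participant stays in follow-up. This stands, and it narrows the conflict to study treatment. It does not remove it, because section 7.2 makes no exception for pregnancy.

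On reporting, a reader might infer that required SAEs are bound to be missed, or that the undertaking in 8.4.5 cannot be met. The document does not support that. The duty in 8.4.5 has no time limit, a pregnancy form goes to the sponsor, section 8.4.1 requires notice of related SAEs learned of later, section 8.4.3 follows an SAE once it is reported, and the Schedule of Activities shows a review at visit 7. What remains is that the later-notice duty is narrower than 8.4.5: it covers only events that the investigator happens to learn of and considers related.

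A reader might also infer that most pregnancy outcomes of every kind fall outside the window. The arithmetic supports this for term and near-term outcomes, or after withdrawal at confirmation, but not for early losses in a participant who stays.

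**Conclusion.** The contradiction is established from the text alone: sections 8.3.4, 10.1 (with exclusion criterion 5), 7.2 and 8.4.5 cannot all be applied to the same participant, and they must be reconciled. This review takes no view on which clinical rule is right.

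The reporting gap is also real, in the form that outcomes may be missed. About 73% of term outcomes and 67% of those at day 245 fall after visit 6, compared with about 12% to 19% of early losses. These figures assume uniform conception over 12 months and continued participation. With withdrawal at confirmation, nearly all outcomes fall after active collection.

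The number of participants affected is probably small. Taking 0 to 2 of 50 as an assumption, that is at most 2/50 = 4% of the sample. The effect on the primary HRQoL comparison is minor. The case rests on participant safety, consistent conduct across investigators and completeness of SAE reporting.

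**What to change.** - **One pregnancy rule.** Reconcile 8.3.4, 8.4.5, 7.2 and 10.1 so that a single statement says, separately, what happens to study treatment and what happens to study participation. The sponsor decides the clinical content. The other sections should refer to that statement.
- **Data under that rule.** State which data continue to be collected, with consent, after a pregnancy is confirmed. This should follow from the sponsor's choice on participation and not pre-empt it.
- **End of AE/SAE collection.** Make 8.4.1 and the Schedule of Activities agree on whether collection closes at visit 6 or visit 7.
- **Follow-up to outcome.** Add to 8.4.1 and 8.4.5 that every reported pregnancy is followed to its outcome, with consent, regardless of visit 6 or withdrawal.

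The cost is amendment wording and a follow-up contact for each of the few pregnancies expected. Sample size and the primary analysis are unchanged.

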## 8.3.5. Suicidal Ideation and Behavior Risk Monitoring

Glucocorticoids in replacement doses are not considered to be a CNS-active intervention.

# 8.4. Adverse Events (AEs) Serious Adverse Events (SAEs), and Other Safety Reporting

The definitions of AEs and SAEs can be found in Appendix [3/7].

The investigator and any qualified designees are responsible for detecting, documenting, and recording events that meet the definition of an AE or SAE and remain responsible for following up all AEs that are serious, considered related to the study intervention or study procedures, or that caused the participant to discontinue the study (see Section 7). This includes events reported by the participant.

The method of recording, evaluating, and assessing causality of AEs and SAEs and the procedures for completing and transmitting SAE reports are provided in Appendix [3/7].

## 8.4.1. Time Period and Frequency for Collecting AE and SAE Information

All SAEs and AEs will be collected from the start of study intervention until visit 6 at the time points specified in the SoA (Section 1.3).

All SAEs will be recorded and reported to the sponsor or designee immediately and under no circumstance should this exceed 24 hours, as indicated in Appendix [3/7]. The investigator will submit any **updated SAE data to the sponsor within 24 hours** of it being available.

Investigators are not obligated to actively seek information on AEs or SAEs after conclusion of the study participation. However, if the investigator learns of any SAE, including a death, at any time after a participant has been discharged from the study, and the investigator considers the

© 2015-2021 TransCelerate BioPharma

Doc. No. CT 2.01.01. Valid from 31 Jan 2022.

Only the electronic version is valid.

Page 39 of 65

event to be reasonably related to the study intervention or study participation, the investigator must promptly notify the sponsor.

## 8.4.2. Method of Detecting AEs and SAEs

Care will be taken not to introduce bias when detecting AEs and/or SAEs. Open-ended and non-leading verbal questioning of the participant is the preferred method to inquire about AE occurrences.

## 8.4.3. Follow-up of AEs and SAEs

After the initial AE/SAE report, the investigator is required to proactively follow each participant at subsequent visits/contacts. All SAEs will be followed until resolution, stabilization, the event is otherwise explained, or the participant is lost to follow-up (as defined in Section 7.3). Further information on follow-up procedures is provided in Appendix 3.

### 8.4.4. Regulatory Reporting Requirements for SAEs

- Prompt notification by the investigator to the sponsor of an SAE is essential so that legal
  obligations and ethical responsibilities towards the safety of participants and the safety of
  a study intervention under clinical investigation are met.
- The sponsor has a legal responsibility to notify both the local regulatory authority and other regulatory agencies about the safety of a study intervention under clinical investigation. The sponsor will comply with country-specific regulatory requirements relating to safety reporting to the regulatory authority, institutional review boards (IRBs)/independent ethics committees (IECs), and investigators.
- An investigator who receives an investigator safety report describing an SAE or other specific safety information (eg, summary or listing of SAEs) from the sponsor will review and then file it along with the Investigator Brochure (IB) investigational directions for use (IDFU) or state other documents] and will notify the Institutional Review Board (IRB) and Institutional Ethics Committee (IEC), if appropriate according to local requirements.
- Investigator safety reports must be prepared for suspected unexpected serious adverse reactions (SUSARs) according to local regulatory requirements and sponsor policy and forwarded to investigators as necessary.

### 8.4.5. Pregnancy

Pregnancy at screening and planned pregnancy during the duration of study
participation is an exclusion criteria. However, all AD patients (including all study
participants) need to continue using one of the study drugs throughout the pregnancy
as cortisol is a hormone necessary for survival in this patient group. The two study
drugs in this study are the only approved treatment options in Norway. Therefore,

© 2015-2021 TransCelerate BioPharma

Doc. No. CT 2.01.01. Valid from 31 Jan 2022. Only the electronic version is valid.

Page 40 of 65

study participants who become pregnant during this trial will not be discontinued from study treatment.

- Pregnant AD patients may need alterations of doses which will be performed by local study investigators independently of study participation.
- If a pregnancy is reported during the study, the investigator will record pregnancy information in the appropriate form and submit it to the sponsor.
- While pregnancy itself is not considered to be an AE or SAE, any pregnancy complication or elective termination of a pregnancy for medical reasons will be reported as an AE or SAE.
- Abnormal pregnancy outcomes (e.g. spontaneous abortion, fetal death, stillbirth, congenital anomalies, ectopic pregnancy) are considered SAEs and will be reported as such.

## **8.5.** Pharmacokinetics

Serum/saliva/urine/hair samples will be collected for measurement of cortisol and metabolites as specified in the SoA (Section 1.3)

## 8.6. Pharmacodynamics

Pharmacodynamics are not evaluated in this study.

## 8.7. Genetics

Genetics are not evaluated in this study.

#### 8.8. Biomarkers

- 21-hydroxylase autoantibodies are assayed to diagnose the etiology of primary adrenal insufficiency.
- TPO antibodies are assayed to diagnose any thyroid comorbidity in PAI patients.
- Biomarkers of cardiovascular health and bone health are given in the protocol.
   BDNF, biomarker of brain plasticity in serum

## 8.9. Immunogenicity Assessments

Immunogenicity to the study drugs is not a clinical problem

© 2015-2021 TransCelerate BioPharma

Doc. No. CT 2.01.01. Valid from 31 Jan 2022. Only the electronic version is valid.

Page 41 of 65

The statistical analysis plan will be finalized prior to inclusion of the first participant and it will include a more technical and detailed description of the statistical analyses described in this section. This section is a summary of the planned statistical analyses of the most important endpoints including primary and key secondary endpoints.

## 9.1. Statistical Hypotheses

Table 4 includes all objectives with corresponding hypothesis and statistical analyses.			
Number	Objective	Hypotheses	Statistical analysis
	Primary		
1.1	Is improvement of HRQoL in PAI patients treated with Plenadren better than improvement of HRQoL in PAI patients treated with Cortisone after 6 and 12 months?	Null hypothesis:  H 0 : $P_{Plen(0-12)} = P_{Cort(0-12)}$ Alternative hypothesis:  H 1 : $P_{Plen0-12} \neq P_{Cort0-12}$ $P_{Plen (0-12)}$ : Increase in HRQoL score from Baseline to 6 and 12 months in Plenadrentreated patients $P_{Cort(0-12)}$ : Increase in HRQoL score from Baseline to 6 and 12 months in Cortisontreated patients	Between group comparison of longitudinal change in HRQoL score by linear mixed effect models for repeated measures.
	Secondary		
2.1	Is there a between group difference in clinical markers of cardio-metabolic health between patients receiving Plenadren and conventional thrice daily Cortisone for 12 months?	Null hypotheses: There is no difference in clinical markers of cardio-metabolic health between patients receiving Plenadren and	Comparing between-group clinical characteristics (BP, BW, BWC, BMI), lipids, glucose and HOMA index between Plenadren-treated and Cortison-treated patients.

© 2015-2021 TransCelerate BioPharma

Doc. No. CT 2.01.01. Valid from 31 Jan 2022.

Only the electronic version is valid.

Page 42 of 65

## CONFIDENTIAL The CORTAD study Clinical Trial Protocol version6.2, 15thNovember 2023

		patients receiving Cortisone	Statistical analysis of paired non- parametric data; i.e. Mann-Whitney U test.
2.2	Is there a difference in hair cortisol concentration in patients receiving Pleandren compared to patients receiving Cortisone at 12 months after treatment initiation?	Null hypotheses: There is no difference in hair cortisol concentration between patients receiving Plenadren and patients receiving Cortisone	Statistical analysis of paired non-parametric data; i.e. Mann-Whitney U test.
2.3	Is there a difference in salivary cortisol day curves in patients receiving Plenadren and conventional Cortisone at 12 months after treatment initiation?	Null hypothesis: There is no betweengroup difference in salivary cortisol AUC	Statistical analysis of paired non-parametric data; i.e. Mann-Whitney U test.
2.4	Is there a difference in the urinary cortisol metabolome in patients receiving Plenadren compared to patients receiving Cortisone at 12 months after treatment initiation?	Null hypothesis: There is no betweengroup difference in urine cortisol metabolome	Statistical analysis of paired non-parametric data; i.e. Mann-Whitney U test.
2.5	Is there a difference in change of sleep score in patients receiving Plenadren and patients receiving Cortisone 6 and 12 months after treatment initiation	Null hypothesis: There is no betweengroup difference in changes of sleep score from baseline to 6 and 12 months of treatment	Between group comparison of longitudinal change in sleep score by linear mixed effect models for repeated measures.
2.6	Is there a difference in sleep quality between patients receiving Plenadren and patients receiving Cortisone at 12 months?	Null hypothesis: There is no betweengroup difference in sleepquality	Statistical analysis of paired non- parametric data; i.e. Mann-Whitney U test
2.7	Is there a difference in cognitive function in patients receiving Plenadren and	Null hypothesis: $H_0$ : $P_{Plen(0-12)} = P_{Cort(0-12)}$	Between group comparison of longitudinal change in cognitive test

© 2015-2021 TransCelerate BioPharma

Doc. No. CT 2.01.01. Valid from 31 Jan 2022.

Only the electronic version is valid.

Page 43 of 65

	patients receiving Cortisone at 1, 6 and 12 months after treatment initiation?	Alternative hypothesis: $H_1$ : $P_{Plen0-12} \neq P_{Cort0-12}$ $P_{Plen (0-12)}$ : Increase in cognitive test scores from Baseline to 6 and 12 months in Plenadrentreated patients $P_{Cort(0-12)}$ : Increase in cognitive test scores from Baseline to 6 and 12 months in Cortisontreated patients	scores by linear mixed effect models for repeated measures
2.8	Is there a difference in change of bone markers in patients receiving Plenadren and patients receiving Cortisone 6 and 12 months after treatment initiation	Null hypothesis:  There is no betweengroup difference in changes of bone markers from baseline to 6 and 12 months of treatment	Between group comparison of longitudinal change bone markers by linear mixed effect models for repeated measures
2.9	BMD/Body composition	Null hypothesis:  There is no betweengroup difference in changes of bone mineral density and body composition from baseline to 12 months of treatment	Between group comparison of longitudinal change in bone mineral density and body composition by linear mixed effect models for repeated measures

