# CONFIDENTIAL The CORTAD study Clinical Trial Protocol version6.2, 15thNovember 2023

Procedure	ng ation			Intervention Period				
	Screening	Randomization	Baseline	Phone visit	Lab visit			
Visit number	1		2	3	4	5	6	7
Diagnostic laboratory tests adrenal insufficiency 	X							
Laboratory tests (hematology, electrolytes, creatine, liver enzymes, cholesterols and triglycerides, HbA1c, cobalamine, , ferritin, renin, aldosterone, 25OH vitamin D, TSH, FT4)			X			X	X	
HOMA index (insulin and glucose)			X			X	X	
Serum and EDTA samples for Biobanking forc- peptide, bone markers, BDNF, metylmalomic acid and autoantibody screening (etiology and autoimmune comorbidity)			X			X	X	
Urine sample (steroid metabolome)							X	
Hair sample (cortisol)			X				X	
HRQoL questionnaires (RAND-36, AddiQoL-30)			X		X	X	X	
Cognitive tests	X					X	X	
Bone mineral density and body composition					X		X	
Blood sampling 1 and 4 h after morning dose (S-cortisol)					X			
Dose adjustment according to S-cortisol (if applicable) 					X			
Saliva cortisol (before, +1h and +4 h after morning dose						X	X	

© 2015-2021 TransCelerate BioPharma

Doc. No. CT 2.01.01. Valid from 31 Jan 2022.

Only the electronic version is valid.

Page 12 of 65

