### Evaluation of bone health:

- Differences in markers of bone health in patients receiving Plenadren and conventional Cortisone at time of diagnosis and 12 months after treatment initiation.
  - Vitamin D
  - N-terminal propertide of type 1 procollagen (P1NP)
  - Bone mineral density (BMD) and Body composition

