### Visit 4 - 1 month

- Physician/ nurse: Interview the patient on the effect of the medication by filling out the adrenal insufficiency form in Noklus Diabetes.
- Patient: Fill in PROMS, including HRQoL questionnaires.
- Note any side-effects, adrenal crisis, infections, or any new concomitant disease and their treatment.
- Blood sampling is performed for serum cortisol 1 and 4 hours after intake of GC replacement morning dose for evaluation and adjusting of the dosage.
- Bone mineral density measurement, body composition, and measure bone markers as well as vitamin D.

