### 8.2.5. Urine sampling

Urine will be sampled for 24 h for analysis of urine cortisol and metabolites (LCMSMS) at visit 5 and 6. Sampling will start early morning with an empty bladder and continue collecting to include the first void the next morning. The participant will measure and register the 24 h urine volume and bring a small sample (10 mL) for analysis.

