## 8.2.8. Sleep

Evaluation of sleep will be performed for one week in between visit 5 and 6:

**Actiwatch Spectrum** (Philips), a watch-like accelerometer and photodiode sensor placed on the wrist, will continuously provide information about motor activity, sleep (sleep timing and efficiency), and light exposure (white and colored light) during the experimental protocol. Data can be converted to objective sleep parameters (25)

**Sleep radar**: Sleep quality will be assessed by a newly developed Norwegian Sleep Radar based on radio ultra wideband pulse-doppler radar technology enables long-term non-invasive sleep recording (Somnofy, Vital Things AS). The sleep algorithm has been validated to provide sleep stage classification with a precision close to what can be achieved using brain activity monitoring using deep neural networks machine learning (26).

**Sleep diary**: SurveyXact will be used in consultation with sleep researchers in University of Bergen.

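### Secondary hypotheses 2.9 (bone density and body composition) and 2.5 (sleep) test change from a baseline that the visit schedule does not measure

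*Protocol*

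**What the plan says.** **DXA.** Hypothesis 2.9 (section 9.1, Table 4) is "There is no betweengroup difference in changes of bone mineral density and body composition from baseline to 12 months of treatment". Its analysis is a comparison of "longitudinal change in bone mineral density and body composition by linear mixed effect models for repeated measures". Section 3, under bone health, gives the timing as "Differences in markers of bone health in patients receiving Plenadren and conventional Cortisone at time of diagnosis and 12 months after treatment initiation", and bone density and body composition are on the list that follows. In the Schedule of Activities (section 1.3) the row "Bone mineral density and body composition" is marked at visits 4 and 6 only. Section 8.1.3 agrees. Its visit 4 list contains "Bone mineral density measurement, body composition, and measure bone markers as well as vitamin D", the same tasks recur at visit 6, and visit 5 has no scan. The screening and inclusion task list in section 8.1.1 contains no DXA.

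**Sleep.** Hypothesis 2.5 is "There is no betweengroup difference in changes of sleep score from baseline to 6 and 12 months of treatment", to be analysed with a repeated-measures mixed model. Section 8.2.8 says "Evaluation of sleep will be performed for one week in between visit 5 and 6". Hypothesis 2.6 separately compares sleep quality between arms at 12 months.

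**The concern.** Both hypotheses need a measurement taken before the randomised drug starts, and none is scheduled. For 2.9, the first scan comes after four weeks on the assigned drug. If the analyst treats it as baseline, any difference between arms that has already developed is subtracted from the result. For 2.5, no within-participant change from baseline exists to be modelled.

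This is not a detail that a statistical analysis plan can settle, because such a plan cannot supply measurements that were never scheduled. Section 8 requires sites to adhere to the Schedule of Activities, so they will follow it as it stands. A scan missed before treatment cannot be recovered, and about 50 participants with a rare disease are planned.

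**Working it through.** **Reading the schedule.** I counted each row's cells against the visit-number row. As a check on the alignment, the HRQoL row falls on visits 2, 4, 5 and 6, which matches the baseline, 1, 6 and 12 months in section 8.2.1. On the same count DXA falls on visit 4 (day 28) and visit 6 (day 365).

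| Source | Timing of bone density / body composition |
|---|---|
| Section 9.1, objective 2.9 | baseline to 12 months |
| Section 3, bone health | diagnosis, 12 months |
| Section 3, cardio-metabolic health (body composition) | diagnosis, 6, 12 months |
| Objectives tables, sections 1.1 and 3 | 1, 6, 12 months |
| Section 1.3 and section 8.1.3 | 1, 12 months |

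No place defines the 1-month scan as the baseline.

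**What the DXA contrast estimates.** Let d1 and d12 be the expected between-arm differences at months 1 and 12. Before the assigned drug starts, the expected difference is 0 by randomisation.

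- Change from a true baseline: d12 − 0 = d12.
- Change from the month-1 scan: d12 − d1.
- Share of d12 left out: d1 / d12.

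The observable interval is 365 − 28 = 337 days, and 337/365 = 92%. The documents give no time course, so the share left out has to be assumed:

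- Linear growth: 28/365 = 7.7%, about 8%.
- Exponential approach with time constant τ: (1 − exp(−28/τ)) / (1 − exp(−365/τ)). This gives 17% for τ = 180 days, 27% for 90, 37% for 60 and 61% for 30.

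If d1 and d12 have opposite signs, d12 − d1 is larger in size than d12, and the contrast is inflated rather than attenuated.

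**What is unaffected.** Section 9.2.1 also plans model-predicted differences between arms at individual visits. The 12-month difference estimates d12 and does not subtract month 1. Only the treatment-by-time (month 1 to 12) contrast is affected.

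**Sleep.** The timings given are:

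- one week between visits 5 and 6 (section 8.2.8);
- visit 5 or visit 6 (section 8.1.3);
- a diary at visits 5–6 (section 8.2.1);
- a diary and actigraphy bar across visits 5 and 6, with the radar at visit 6 (section 1.3);
- 6–12 months (section 3).

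None gives a measurement at screening, baseline or 1 month. Even if the looser entries are read as two recordings, the only change available is from 6 to 12 months, which is not the one 2.5 states. With one recording there is no change at all.

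**The case against.** The strongest reply is about consequence. Both hypotheses are secondary, and section 9.3 makes no power calculation for them. The primary HRQoL endpoint does have a visit 2 measurement. The randomised 12-month scan is kept, so for 2.9 the fault is a wrongly named reference visit and not a lost endpoint. Row 2.5 largely duplicates 2.6, and section 3 promises sleep only at 6–12 months. All of this stands, and it limits the weight of the point without removing the contradiction.

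A reader might infer more than the documents support:

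- **That the DXA result is biased toward no difference.** This holds only for the month 1 to 12 contrast, and only if early and late effects share a direction.
- **That half or more of the effect is lost.** No figure in the protocol supports such a share. Even the 8% assumes linear growth, and the larger values above rest on assumed time constants.
- **That the 6-month urine endpoint is lost.** Section 8.2.5 says "Urine will be sampled for 24 h for analysis of urine cortisol and metabolites (LCMSMS) at visit 5 and 6" and section 8.1.3 also collects urine at both visits. The Schedule of Activities marks visit 6 only. Hypothesis 2.4 tests 12 months, so no tested comparison is lost.
- **That cognition lacks data for its test.** The objectives tables and the question in 2.7 mention 1 month, which is not scheduled. The quantities in 2.7 are defined from baseline to 6 and 12 months, and testing is scheduled at screening and at visits 5 and 6.

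One could also argue that glucocorticoid treatment of under 31 days before inclusion (section 5.1) already spoils any baseline. It does not affect the comparison between arms: it precedes the randomised drug and is balanced in expectation, whereas the 28 days on the assigned drug are not. It does mean that a visit 2 scan is not strictly one at diagnosis.

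**Conclusion.** The point holds as an internal contradiction affecting two secondary hypotheses. For 2.9, the estimable change is month 1 to month 12 and covers 337 of 365 days. It omits about 8% of the 12-month difference under an assumed linear course, and more if the effect comes early. Attenuation depends on early and late effects having the same sign. The between-arm difference at 12 months is sound. For 2.5, the stated change cannot be estimated under any of the protocol's sleep timings, and only a between-arm comparison of the kind in 2.6 remains. The sleep conclusion needs no numerical assumption. The urine and cognition mismatches are minor matters of consistency.

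**What to change.** 1. **DXA.** Choose one of two options.
   - Move the visit 4 scan to visit 2, before the assigned drug starts, in sections 1.3 and 8.1.3. This needs no extra scan; the cost is fitting it into the inclusion window.
   - Leave the schedule and restate 2.9 as a between-arm comparison at 12 months. This changes wording only.
2. **Common analysis.** Under either option, use the 12-month between-arm comparison for all participants. Adjust for a pre-treatment scan only if every participant has one. Do not label a month-1 scan as baseline. This avoids splitting the roughly 50 participants between two analyses if some have already been scanned at month 1.
3. **Sleep.** Delete 2.5. Keep 2.6 and state one time for it, since it now says 12 months while section 8.2.8 records sleep between visits 5 and 6.
4. **Reconcile the DXA and body-composition timings in one pass.** This covers the objectives tables in sections 1.1 and 3, the cardio-metabolic and bone-health lists in section 3, sections 1.3 and 8.1.3, and row 2.9 of Table 4. Remove the 6-month entries unless a scan is added there. If visit 2 is used, replace the reference to diagnosis.
5. **Minor corrections.** Align 6-month urine between the Schedule of Activities and sections 3, 8.1.3 and 8.2.5. Align the 1-month cognition wording in the objectives tables and row 2.7 with the Schedule of Activities.

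Apart from moving the scan, every change is to wording. If the scan is to move, the amendment should be made promptly, because each participant enrolled beforehand will have no pre-treatment scan.
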